4.1 Study Treatments - Nivolumab/Daratumumab Cohorts

For product descriptions see [Table 4.1-1](#). Non-investigational medicinal product will be used to treat infusion reactions as described in [Section 3.4.2.1](#).

Table 4.1-1: Product Description - Nivolumab/Daratumumab Cohorts, Treatment Period

Product Description and Dosage Form	Potency	IP/ Non IP	Primary Packaging (Volume)/ Label Type	Secondary Packaging (Qty) /Label Type	Appearance	Storage Conditions (per label)
BMS-936558-01 (nivolumab) Solution for injection	100 mg (10 mg/mL)	IP	10 mL vial/ Open-Label	5 or 10 vials per carton/ Open-Label	Clear to opalescent, colorless to pale yellow liquid. May contain particles.	2 - 8°C Protect from light and freezing.
Pomalidomide Capsules*	1 mg, 2 mg, 3 mg, and 4 mg	Non IP	Market Product Configuration	Market Product Configuration	As per US commercial product.	As per Package Insert
Daratumumab Injection for Intravenous Infusion	100 mg (20 mg/mL) and/or 400 mg (20 mg/mL)	IP	Vial	Carton	Colorless to pale yellow solution in a vial.	As per Package Insert/ clinical supply label
Dexamethasone Solution**	4 mg/mL, 8 mg/mg, or other strengths	Non IP	Various Packaging Configurations	Various Packaging Configurations	Various	As per Package Insert
Dexamethasone tablets**	2 mg, 4 mg, or other strengths	Non IP	Various Packaging Configurations	Various Packaging Configurations	Various	As per Package Insert

IP= investigational product

*Pomalidomide should be obtained by the investigator sites standard prescribing procedures where allowed.

**Dexamethasone solution and tablets will be procured by the investigative sites.

4.1.1 Investigational Product

4.1.1.1 Nivolumab in the Nivolumab/Daratumumab Cohorts

Cohort A subjects: nivolumab will be administered at a dose of 240 mg as an intravenous infusion over 30 minutes every 2 weeks (Day 15 of Cycle 1, and Days 1 and 15 of each 28 day cycle during Cycles 2 through 6). Starting Cycle 7 and beyond, nivolumab will be administered at a dose of 480 mg as an intravenous infusion over 30 minutes every 4 weeks (Day 1 of each 28 day cycle).

Cohort B subjects: randomized to ND treatment (only): nivolumab will be administered at a dose of 240 mg as an intravenous infusion over 30 minutes on Day 15 of Cycle 1. Starting Cycle 2 and beyond, nivolumab will be administered at a dose of 480 mg as an intravenous infusion over 30 minutes every 4 weeks (Day 1 of each 28 day cycle).

Please refer to the nivolumab investigator brochure and/or pharmacy reference sheet/manual for guidelines on drug preparation and administration. Flush the intravenous line at the end of infusion.

4.1.1.2 Daratumumab

Daratumumab injection for IV infusion is considered IMP for this study. Daratumumab vials must be stored in accordance with the package insert (USPI) /clinical supply labeling.⁷⁰

Daratumumab is an immunoglobulin G1 kappa (IgG1 κ) human monoclonal antibody against CD38 antigen, produced in a mammalian cell line (Chinese Hamster Ovary [CHO]) using recombinant DNA technology. The molecular weight of daratumumab is approximately 148 kDa.

Daratumumab is supplied as a colorless to pale yellow preservative-free solution for intravenous infusion in single-dose vials. Daratumumab must be diluted with 0.9% Sodium Chloride Injection, USP and to be administered as IV infusion according to the infusion rates specified in the (USPI)/pharmacy reference manual.⁷⁰

Daratumumab can cause severe infusion reactions, where about half of all patients in the studies to date experienced a reaction, most during the first infusion. Infusion reactions can also occur with subsequent infusions. Nearly all reactions occurred during infusion or within 4 hours of completing the daratumumab infusion.

Because of this high risk of infusion related reactions daratumumab infusions will be administered per the approved (USPI)/pharmacy reference manual⁷⁰ by a healthcare professional, with immediate access to emergency equipment and appropriate medical support to manage infusion reactions if they occur, and all subjects will receive pre-infusion and post-infusion medication per the approved (USPI)/pharmacy reference manual.⁷⁰

Before administration the drug product should be stored and prepared as per the instructions in current (USPI)/pharmacy reference manual.⁷⁰ The dose of daratumumab to be administered to a

subject will be calculated by multiplying the subject's weight (kg) by 16 mg/kg. The subject's predose weight on Day 1 of each cycle will be used to calculate the dose for each cycle. The dose does not need to be recalculated for weight changes that are < 10% from baseline. Each dose should be infused as per instructions in the current daratumumab (USPI)/pharmacy reference manual.⁷⁰

For the administration of the first 16 mg/kg dose of daratumumab, in addition to previously approved single first infusion on Cycle 1 Day 1, a split-dosing regimen (ie, splitting the first dose over two consecutive days at 8 mg/kg on Cycle 1 Days 1 and 2) was recently approved in EU, US, and Canada. Investigators are allowed to opt for the split-dosing regimen.

The infusion start and stop time will be recorded in the CRF. If the infusion is stopped mid-session for any reason, the stop/start time must be recorded together with an explanation.

Indirect Antiglobulin Test (IAT)

Blood Type, Rh, and IAT should be done before the first dose of daratumumab. Subject RBC phenotyping (standard or extended) is an alternative option to the IAT test, if locally required. Either method must be completed prior to first daratumumab infusion.

Daratumumab interferes with the Indirect Antiglobulin Test (IAT), which is a routine pre-transfusion test performed to identify a patient's antibodies to minor antigens so that suitable donor blood can be given for transfusion. Daratumumab does not interfere with /RhD typing. CD38 is expressed at very low levels on erythrocytes. Daratumumab binds to the CD38 on erythrocytes, which results in a positive IAT (also known as the Indirect Coombs Test). This positive result masks the detection of antibodies to minor antigens and may prevent or delay blood banks from issuing donor blood for transfusion. This effect occurs during daratumumab treatment and for up to 6 months after treatment ends. Subjects will receive a patient identification wallet card for the study that includes the blood profile (ABO, Rh, and IAT or phenotyping) determined before the first infusion of daratumumab along with information on the IAT interference for healthcare providers/blood banks. Subjects are to carry this card throughout the treatment period and for at least 6 months after treatment ends. Blood banks can eliminate the daratumumab IAT interference with IAT by treating reagent RBCs with dithiothreitol (DTT).¹⁰²

Possible methods for blood banks to provide safe RBCs for transfusion to subjects receiving daratumumab include:

- 1) Providing ABO/RhD compatible, phenotypically (standard or extended phenotyping) or genotypically matched units
- 2) Providing ABO/RhD compatible, K-negative units after ruling out or identifying alloantibodies using DTT-treated reagent RBCs.

Uncrossmatched, ABO/RhD compatible RBC units should be administered if transfusion is needed emergently as per local blood bank practice.

Despite daratumumab binding to CD38 on erythrocytes, no indication of clinically significant hemolysis has been observed in daratumumab studies. For additional details, refer to the Daratumumab IB/package insert.

4.1.2 Noninvestigational Product

In this protocol, non-investigational products consist of:

- Pomalidomide (Pomalyst®) capsules 1 mg, 2 mg, 3 mg, and 4 mg
- Dexamethasone tablets and concentrate for solution for IV infusion
- Products used for daratumumab pre- and post-infusion medication (refer to [Section 3.4.1.4](#) and (USPI)/pharmacy reference manual).⁹⁸

4.1.2.1 Pomalidomide

Pomalidomide is an analogue of thalidomide. Thalidomide is a known human teratogen that causes severe life-threatening human birth defects. If pomalidomide is taken during pregnancy, it may cause birth defects or death to an unborn baby. Females must not get pregnant: (1) for at least 4 weeks before starting pomalidomide, (2) while taking pomalidomide, (3) during any interruptions in pomalidomide treatment and (4) for at least 4 weeks after their last dose of pomalidomide. Furthermore, subjects taking pomalidomide should refrain from donating blood (until at least 90 days) or sperm (until at least 4 weeks) after last dose of pomalidomide.

Because of this potential toxicity and to avoid fetal exposure to pomalidomide, pomalidomide is only available under a special restricted distribution program. Each risk management program is country or region specific. Under these programs, only prescribers and pharmacists registered with the program can prescribe and dispense the product. In addition, pomalidomide must only be dispensed to subjects who are registered and meet all the conditions of the local pomalidomide risk management program or meet all the conditions of the Pomalidomide Pregnancy Risk Prevention Plan. Subjects who have the potential of pregnancy must be instructed about contraception and undergo the scheduled pregnancy tests. Pomalidomide should be taken in accordance with local label.

WOCBP must have negative pregnancy testing and must use contraception methods before initiating pomalidomide.

4.1.2.2 Dexamethasone

Dexamethasone tablets and solution for IV infusion is considered non-IMP for this study. Marketed product will be utilized for this study and should be stored in accordance with the package insert.¹⁰³

4.1.3 Study Drug Storage, Preparation and Administration

Please refer to the current version of the IB and/or pharmacy reference sheets for complete storage, handling, dispensing, and infusion information for nivolumab, and to the current (USPI)/pharmacy reference manual⁹⁸ for daratumumab, and dexamethasone IV.

Nivolumab vials must be stored at a temperature of 2° to 8°C and should be protected from light and freezing. If stored in a glass front refrigerator, vials should be stored in the carton. Recommended safety measures for preparation and handling of nivolumab include laboratory coats and gloves. For details on prepared drug storage and use time of nivolumab under room temperature/light and refrigeration, please refer to the nivolumab IB section for “Recommended Storage and Use Conditions” and/or pharmacy reference sheets.

Nivolumab injection is to be administered as an IV infusion through a 0.2-micron to 1.2-micron pore size, low-protein binding polyethersulfone membrane in-line filter at the protocol-specified doses. It is not to be administered as an IV push or bolus injection. Nivolumab injection can be infused undiluted (10 mg/mL) or diluted with 0.9% Sodium Chloride Injection, USP or 5% Dextrose Injection, USP to protein concentrations as low as 1 mg/mL. Care must be taken to assure sterility of the prepared solution as the product does not contain any antimicrobial preservative or bacteriostatic agent.

Daratumumab infusion solution will be prepared as a 1,000-mL (first dose, unless using split dose) or 500-mL (second and subsequent doses) dilution of daratumumab in sterile, pyrogen-free 0.9% Sodium Chloride Injection, USP. Preparation of infusion bags should be done on the day of the planned infusion. Daratumumab must be administered as an IV infusion given through a well-functioning IV catheter by using an infusion pump or syringe pump. Daratumumab must be filtered by using an inline filter (0.2 µM) during the infusion. Manuals with detailed descriptions for preparation and administration of daratumumab will be supplied to each pharmacy and site.

In addition to administering a full dose of 16 mg/kg on Cycle 1 Day 1, “split-dosing” of daratumumab (ie, 8 mg/kg on Cycle 1 Day 1 and 8 mg/kg on Cycle 1 Day 2) can be utilized for Cohort B at the investigator’s discretion. The first split-dose infusion will be prepared as a 500-mL dilution of 8 mg/kg of daratumumab given on Days 1 and 2 of Cycle 1. If these 2 infusions are well-tolerated (absence of > Grade 1 IRR), the second week of daratumumab will be given as a 16 mg/kg dose diluted in 500 cc of normal saline. If the first 2 doses of daratumumab are not well-tolerated (defined as > Grade 1 IRR), then the second week of daratumumab will be given as 16 mg/kg in 1000 mL on Cycle 1 Day 8. From Cycle 1 Day 15 and beyond, the dose of daratumumab will not be split and will be the standard 16-mg/kg dose. The dilution will be in 1000 cc of normal saline until the subject completes an infusion without > Grade 1 IRR. For all infusions, daratumumab will be prepared in sterile, pyrogen free 0.9% NaCl. Preparation of the infusion bags should be done on the day of the planned infusion. Daratumumab must be administered as an IV infusion given through a well-functioning IV catheter by using an infusion pump. The study drug must be filtered by using an inline filter (0.2 µM) during the infusion. Manuals with detailed descriptions for preparation and administration of daratumumab will be supplied to each pharmacy and site.

Infusion-related supplies (eg, IV bags, in-line filters, 0.9% NaCl solution, pump) will not be supplied by the sponsor and should be purchased locally if permitted by local regulations.

When more than one study drugs are to be administered as IV infusion on the same day, separate infusion bags and filters must be used for each infusion. Nivolumab is to be administered first. The nivolumab infusion must be promptly followed by a saline flush to clear the line of nivolumab before starting the daratumumab infusion. The second infusion will always be daratumumab and will start no sooner than 30 minutes after completion of the nivolumab infusion.

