In addition, these at-risk subjects may be hospitalized for monitoring for up to 2 nights after an infusion. If subjects are hospitalized, then their spirometry test (FEV1) should be performed before discharge. If these subjects are not hospitalized, then a follow up telephone call should be made to monitor their condition within 48 hours after all infusions. If no infusion-related reaction has occurred, the follow-up telephone call 48 hours after the infusion is not required. If the subject has not experienced a significant medical event but is hospitalized overnight only for observation, then the hospitalization should not be reported as a serious adverse event. Investigators may prescribe bronchodilators, H1-antihistamines, and corticosteroids that are deemed necessary to provide adequate supportive care in the event a bronchospasm occurs after subjects are released from the hospital/clinic. If an at-risk subject experiences no major infusion-related reactions, then these post-infusion medications may be waived after 4 doses at the investigator's discretion.

Any post-infusion medication will be administered after the infusion has completed.

Management of Infusion-Related Reactions

- Subjects should be carefully observed during daratumumab infusions. Trained study staff at the clinic should be prepared to intervene in case of any infusion reactions, and resources necessary for resuscitation must be available. Attention to staffing should be considered when multiple subjects will be dosed at the same time.

- For infusion reactions of any grade/severity, immediately interrupt the daratumumab infusion and manage symptoms. Management of infusion reactions may further require reduction in the rate of infusion, or treatment discontinuation of daratumumab.
- Grade 1-2 (mild to moderate): Once reaction symptoms resolve, resume the infusion at no more than half the rate at which the reaction occurred. If the patient does not experience any further reaction symptoms, infusion rate escalation may resume at increments and intervals as appropriate as outlined in [Table 4.1.4.2-1](#).

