- Grade 3 (severe): Once reaction symptoms resolve, consider restarting the infusion at no more than half the rate at which the reaction occurred. If the subject does not experience additional symptoms, resume infusion rate escalation at increments and intervals as outlined in [Table 4.1.4.2-1](#). Repeat the procedure above in the event of recurrence of Grade 3 symptoms. Permanently discontinue daratumumab upon the third occurrence of a Grade 3 infusion-related reaction.
- Grade 4 (life threatening): Permanently discontinue daratumumab treatment.

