4.1.4.2 Daratumumab

Daratumumab will be administered at a dose of 16 mg/kg as an IV infusion every week (Days 1, 8, 15, and 22 of each 28-day cycle) during Cycles 1 and 2. As an option, in Cycle 1, the first full dose of daratumumab at 16 mg/kg may be split into 2 doses at 8 mg/kg and administered via IV on Cycle 1 Days 1 and 2. From Cycles 3 through 6, daratumumab will be administered every 2 weeks (Days 1 and 15 of each 28-day cycle), then starting Cycle 7 and beyond, daratumumab will be administered every 4 weeks (Day 1 of each 28-day cycle). The infusion rates should closely follow the specifications of the currently approved (USPI)/pharmacy reference manual.⁹⁸

All infusions will be planned as outpatient visits. Subjects will receive preinfusion medications and postinfusion medications as detailed in the protocol.

Daratumumab should be administered after nivolumab.

MM subjects randomized to the ND or D regimens will receive pre- and post-infusion medication for daratumumab infusion per the daratumumab label, as described (in [Section 3.4.1.4](#)).

MM subjects randomized to ND-Pd regimen will receive the treatment regimen dexamethasone dose split as IV pre-infusion and oral post-infusion on weeks with daratumumab infusions, and only oral in the weeks without daratumumab infusion (see [Section 4.1.4.4](#)). No additional corticosteroids besides the dexamethasone dose included in the treatment regimen will be administered to the ND-Pd subjects.

The dilution volumes and infusion rates for C1D1 (16 mg/kg), and optional split-dosing of C1D1 (8 mg/kg) and C1D2 (8 mg/kg), C1D8 (16 mg/kg), and subsequent infusions are provided in [Table 4.1.4.2-1](#). The sponsor may modify the infusion rates or the preinfusion medications prospectively based upon the information collected to date from this and other studies. Additional details for administration times and rates, as well as preinfusion medications, will be provided in the administration guidelines (study site investigational product and procedures manual/package insert).

Table 4.1.4.2-1: Daratumumab Infusion Rates

	Dilution Volume	Initial Infusion Rate (first hour)	Increments of Infusion Rate	Maximum Infusion Rate
C1D1 (16 mg/kg single dose)	1000 mL	50 mL/hour	50 mL/hour every hour	200 mL/hour
Optional split-dosing: C1D1 and C1D2 (8 mg/kg split dose)	500 mL	50 mL/hour	50 mL/hour every hour	200 mL/hour

Table 4.1.4.2-1: Daratumumab Infusion Rates

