	Dilution Volume	Initial Infusion Rate (first hour)	Increments of Infusion Rate	Maximum Infusion Rate
C1D8 ^{a,b} (16 mg/kg)	500 mL	50 mL/hour	50 mL/hour every hour	200 mL/hour
Subsequent infusions ^c	500 mL	100 mL/hour	50 mL/hour every hour	200 mL/hour

^a If the subject's first infusion of daratumumab at 16 mg/kg is well-tolerated, subsequent infusions will be administered at an initial rate of 100 mL/hour and increased by 50-mL/hour increments at 60-minute intervals, as tolerated, to a maximum rate of 200 mL/hour.

^b If the subject's first 2 infusions of 8 mg/kg daratumumab are well-tolerated (defined as an absence of IRR >Grade 1), the first infusion of 16 mg/kg daratumumab will be administered at an initial rate of 50 mL/hour and increased by 50-mL/hour increments at 60-minute intervals, as tolerated, to a maximum rate of 200 mL/hour. If the 8 mg/kg infusions are not well-tolerated (defined as IRR >Grade 1), the dose on C1D8 should be given in 1000 mL.

^c Modified rates should only be used if the first 2 16 mg/kg infusions of daratumumab were well-tolerated as defined by an absence of > Grade 1 infusion-related reactions during a final infusion rate of ≥ 100 mL/hr

Vital signs should be monitored extensively throughout daratumumab infusion(s) on Cycle 1 Day 1 (16 mg/kg) or Cycle 1 Days 1 & 2 (split-dosing at 8 mg/kg). For subsequent infusions, vital signs should be measured before the start of the infusion and at the end of the infusion. If a subject experiences any significant medical event, then the investigator should assess whether the subject should stay overnight for observation. If the subject has not experienced a significant medical event but is hospitalized overnight only for observation, then the hospitalization should not be reported as a serious adverse event.

There will be no dose escalations or reductions of daratumumab allowed. Doses of daratumumab may be interrupted, delayed, or discontinued depending on how well the subject tolerates the treatment.

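### For a split-dose subject who reacted at each of the first three daratumumab infusions, Section 4.1.3 requires a 1000 mL bag at C1D15 but Table 4.1.4.2-1 gives 500 mL (minor)

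*Protocol*

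**What the plan says.** Protocol Section 4.1.3 lets the investigator split the first daratumumab dose in Cohort B into 8 mg/kg on C1D1 and 8 mg/kg on C1D2, each in 500 mL. If those infusions bring a reaction above Grade 1, the C1D8 dose is 16 mg/kg in 1000 mL. The section then continues: "From Cycle 1 Day 15 and beyond, the dose of daratumumab will not be split and will be the standard 16-mg/kg dose". The volume rule follows directly: "The dilution will be in 1000 cc of normal saline until the subject completes an infusion without > Grade 1 IRR".

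Protocol Section 4.1.4.2 sends the reader to Table 4.1.4.2-1 for both volumes and rates. It names the infusions covered, ending with "C1D8 (16 mg/kg), and subsequent infusions are provided in" that table. The Subsequent infusions row, which covers C1D15, gives 500 mL, a 100 mL/hour start and a 200 mL/hour maximum. Two footnotes matter here:

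- Footnote b covers split doses that were not well tolerated and says "the dose on C1D8 should be given in 1000 mL". It goes no further than that day.
- Footnote c, attached to the Subsequent infusions row, says "Modified rates should only be used if the first 2 16 mg/kg infusions of daratumumab were well-tolerated". It limits rates and names no other volume.

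The SAP (Section 2.2) gives daratumumab dose and schedule but no dilution volume.

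**The concern.** The two places give different bags for the same subject on the same day. Footnote b carries the C1D8 part of the Section 4.1.3 exception into the table, so a reader preparing the C1D15 dose could reasonably take the table as complete. That reader would prepare 500 mL where Section 4.1.3 requires 1000 mL.

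The table's rates are in mL/hour, so the bag volume fixes the drug delivered per hour. The total dose is 16 mg/kg either way. The subject's three earlier infusions all ran at one concentration. The table's bag would be the first at twice that concentration, given to someone who reacted to all three. What is at stake is how the dose is prepared for a few subjects; no endpoint definition or analysis depends on it.

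**Working it through.** **Can such a subject reach C1D15?** Yes. Under Section 3.4.1.4 a Grade 4 reaction ends daratumumab, and so does a third Grade 3: "Permanently discontinue daratumumab upon the third occurrence of a Grade 3 infusion-related reaction". Three Grade 2 reactions, or up to two Grade 3 with the rest Grade 2, leave the subject on drug. A subject who tolerated C1D1, C1D2 or C1D8 has arguably met the Section 4.1.3 condition and is not counted here.

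**The two instructions at C1D15.**

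| Source | Volume | Reason |
|---|---|---|
| Section 4.1.3 | 1000 mL | No infusion yet completed free of a reaction above Grade 1 |
| Table 4.1.4.2-1, Subsequent infusions | 500 mL | Footnote b stops at C1D8; footnote c concerns rates |

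Footnote a does not help, because it requires the first 16 mg/kg infusion to have been well tolerated.

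**Concentration = dose / volume.**

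- C1D1 and C1D2: 8/500 = 0.016 mg/kg/mL
- C1D8 after reactions: 16/1000 = 0.016 mg/kg/mL
- C1D15 by Section 4.1.3: 16/1000 = 0.016 mg/kg/mL
- C1D15 by the table: 16/500 = 0.032 mg/kg/mL

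**Delivery = concentration × pump rate (mg/kg/h).**

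| Pump rate (mL/hour) | 500 mL bag | 1000 mL bag |
|---|---|---|
| 50 | 1.6 | 0.8 |
| 100 | 3.2 | 1.6 |
| 150 | 4.8 | 2.4 |
| 200 | 6.4 | 3.2 |

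The ratio is 0.032/0.016 = 2 at every rate. Footnote c withholds the 100 mL/hour start from this subject and names no fallback. The 50 mL/hour line is therefore an equal-rate comparison, not a rate the table prescribes for C1D15.

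**Infusion time**, uninterrupted from 50 mL/hour, rising 50 each hour to 200. The first three hours deliver 50 + 100 + 150 = 300 mL.

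- 500 mL: 3 + 200/200 = 4.0 hours
- 1000 mL: 3 + 700/200 = 6.5 hours

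**How many subjects?** The documents give no figure. Section 4.1.1.2 says only that "about half of all patients in the studies to date experienced a reaction, most during the first infusion", at any severity. For illustration, take 60 subjects × split-dose uptake × chance of a reaction above Grade 1 on C1D1 × again on C1D2 × again on C1D8. Every factor after the 60 is assumed, with the C1D1 rate kept below one half.

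- Low: 60 × 0.25 × 0.20 × 0.20 × 0.05 = 0.03
- Middle: 60 × 0.50 × 0.30 × 0.35 × 0.125 = 0.39
- High: 60 × 0.75 × 0.40 × 0.50 × 0.20 = 1.8

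That is about 0 to 2 subjects. The 60-fold spread (1.8/0.03) shows how little is known. Because most reactions come at the first infusion, the high case is the least plausible.

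**The case against.** The strongest reply is that a specific rule governs a general default. Section 4.1.3 speaks to split-dose subjects who keep reacting, and the table row states the ordinary volume. Read together they give 1000 mL until one infusion is tolerated, then 500 mL. Footnote c also suggests that the row was written for subjects who tolerate the drug. This stands as a way to resolve the conflict, and 1000 mL is the right answer. It does not make the table correct. The table is named as the source of volumes for these infusions, repeats only part of the exception, and has no note on the row pointing back to Section 4.1.3. The general 500 mL default within Section 4.1.3 itself is different: the split-dose text follows it there, so it is not counted as a conflict.

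The protocol also relies on pharmacy and site manuals that were not available. They may already specify 1000 mL, in which case nothing would go wrong in practice. They cannot satisfy both protocol texts.

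A reader might infer three stronger things that the documents do not support:

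- *The restart safeguard is defeated.* It is not. Section 3.4.1.4 says to "resume the infusion at no more than half the rate at which the reaction occurred", which refers to the bag in use. A reaction at 150 mL/hour from the 500 mL bag occurs at 4.8 mg/kg/h, and a restart at 75 mL/hour gives 75 × 0.032 = 2.4. Delivery is halved in full.
- *Reaction management steers staff to the wrong volume.* Section 3.4.1.4 refers to the table for rate steps after a reaction, when the bag is already made. No volume is chosen then.
- *The 500 mL bag is unsafe in itself.* It is the ordinary preparation for later infusions. Premedication, interruption for a reaction of any grade, and the discontinuation rules all still apply.

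**Conclusion.** Minor, but wrong as written. For a split-dose Cohort B subject still on daratumumab after reactions above Grade 1 at C1D1, C1D2 and C1D8, Table 4.1.4.2-1 gives half the volume that Section 4.1.3 requires at C1D15. The twofold difference in mg/kg/h at an equal pump rate is exact and rests only on the stated doses and volumes. The number of subjects rests on assumption, and few if any should be expected. The documents do not show that anyone would actually receive the wrong bag, because the manuals were not available and Section 4.1.3 should prevail when both places are read.

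**What to change.** Add a footnote to the Subsequent infusions row of Table 4.1.4.2-1: for split-dose subjects whose C1D8 dose was given in 1000 mL, keep 1000 mL until one infusion has been completed with no IRR above Grade 1 (see Section 4.1.3). Check that the pharmacy manual says the same.

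This carries over a rule that the protocol already contains. The cost is the longer infusion shown above, 2.5 hours more (6.5 − 4.0) each time if uninterrupted from 50 mL/hour, for these few subjects until one infusion is tolerated.
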